Exposure:	4 th vaccine dose/2 nd booster dose of Comirnaty or Spikevax
Comparator:	No 4 th vaccine dose/2 nd booster dose (only 3 rd dose)
Outcome:	COVID-19 related hospitalisation;COVID-19 related death
Time (when follow up begins and ends):	Follow-up start: at index date of matched 3-dose vaccinated/4-dose vaccinated people after start of roll-out of vaccination programs for 2nd booster dose End of follow-up: End of their observation (i.e. date of data extraction, database availability or death), next vaccine dose or outcome event, whatever comes first.
Setting:	Primary care electronic health records from SIDIAP [Spain], IPCI [The Netherlands] and CPRD GOLD [UK]
Main measure of effect:	Vaccine effectiveness, calculated as 1 - Hazard ratio (HR)

B. Primary research question: Objectives 3

	Phase II C3-002 – Study Protocol	
	Author(s): [name], [name], [name]	Version: v2.1
	Dissemination level: Public	

Outcome:	To assess the effectiveness of COVID-19 vaccination for the prevention of post-acute all-cause mortality in the 3- and 6-months following discharge for COVID-19 related hospitalisation
Hypothesis:	NA
Population (mention key inclusion-exclusion criteria):	All subjects aged 12 years and older, with at least 365 days of data availability in the respective database before index date (ID) with 
 • a 1st-vaccine dose [2nd vaccine dose; 3rd vaccine dose] of Comirnaty or Spikevax. • at least 365days of data availability in the respective database. • at least 90days of time elapsed since the last vaccine dose at the time of study inclusion. • at least 90days of time elapsed since the last record of a clinical diagnosis of COVID-19 or positive SARS-COV-2 test at the time of study inclusion.
Exposure:	2 nd vaccine dose [3 rd vaccine dose; 4 th vaccine dose] of Comirnaty or Spikevax
Comparator:	No 2 nd vaccine dose [3 rd vaccine dose; 4 th vaccine dose] of Comirnaty or Spikevax
Outcome:	All-cause mortality within 3/6months following COVID-19 related hospitalisation

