8.5 Study Population with inclusion and exclusion criteria

The source population will comprise all subjects aged 12 years and older, with at least 365 days of data availability in the respective database before index date (ID) [ID defined as the date of the “latest” vaccine dose administered] AND data availability from 12/2020 onwards (i.e. the time when the roll-out of the vaccination campaign started) in the respective database will be included.

People will then be matched 1:1 based on the number of vaccines doses they received [exposure], with their matched counterparts having 1 vaccine dose less at the time of matching. Based on the index date of matched counterparts, the following inclusion criteria will be applied:

- At least 365 days of data availability in the respective database
- At least 90days of time elapsed since the last vaccine dose for >2 doses), at least 21days of time elapsed since the last vaccine dose for 2 doses and no previous vaccine dose recorded for 1st dose).
- At least 90days of time elapsed since the last record of a clinical diagnosis of COVID-19 or positive SARS-COV-2 test.

For analyses where diabetes mellitus or cardiovascular events are assessed as post-acute COVID-19 complications, people must not have had a record of the outcome within 365days before their index date for cardiovascular events, and no record anytime before index date for diabetes.

Operational definitions of Inclusion and Exclusion Criteria are provided in [Tables 8.5.1](#) and [8.5.2](#).

	Phase II C3-002 – Study Protocol	
	Author(s): [name], [name], [name]	Version: v2
	Dissemination level: Public	

Table 8.5.1. Operational Definitions of Inclusion Criteria

Criterion	Details	Order of application	Assessment window	Care Settings ¹	Code Type	Diagnosis position ²	Applied to study populations:	Measurement characteristics/validation	Source for algorithm
Observation period of 365day prior entry (all cohorts)	Study participants will be required to have 365 days prior history observed before contributing observation time	before	[-365, 0]	n/a	n/a	n/a	All individuals within the selected databases	n/a	n/a
Covid-19 vaccinated: 1 dose only	Exactly 1 Comirnaty/Spikevax vaccination record	after	n/a	OP	RxNorm	n/a			
Covid-19 vaccinated: Completed primary vaccination course	Exactly 2 vaccination records, with the latest being Comirnaty/Spikevax and at least 21days later than the 1st dose.								

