Covid-19 vaccinated: 3 rd dose	Exactly 3 vaccination records, with the 3 rd dose being either monovalent or any of the adapted, bivalent Comirnaty/Spikevax vaccines								
Covid-19 vaccinated: 4 th dose, monovalent or adapted/bivalent	Exactly 4 vaccination records, with the latest being Comirnaty/Spikevax								
Covid-19 vaccinated: 4 th dose, monovalent	Exactly 4 vaccination records, with the 4 rd dose being a monovalent Comirnaty/Spikevax vaccine								
Covid-19 vaccinated: 4 th dose, adapted/bivalent	Exactly 4 vaccination records, with the 4 rd dose being any of the adapted, bivalent Comirnaty/Spikevax vaccines								

OP = outpatient, n/a = not applicable

	Phase II C3-002 – Study Protocol	
	Author(s): [name], [name], [name]	Version: v2.1
	Dissemination level: Public	

Table 8.5.2. Operational Definitions of Exclusion Criteria

Criterion	Details	Order of application	Assessment window	Care Settings ¹	Code Type	Diagnosis position ²	Applied to study populations:	Measurement characteristics/validation	Source for algorithm
At least 90days of time elapsed since the last vaccine dose at the time of study inclusion [3rd, 4 th dose]	Study participants will be required to have at least 90days of time elapsed between their 2 nd and 3 rd , or 3 rd and 4 th vaccine dose.	after	[-90, ID]	OP	RxNorm	n/a	People with 3 rd and 4 th vaccine dose	n/a	n/a
At least 21days of time elapsed since the last vaccine dose at the time of study inclusion. [2 nd dose]	Study participants will be required to have at least 21days of time elapsed between their 2 nd and 1 st , vaccine dose.	after	[-21, ID]	OP	RxNorm	n/a	People with 2 nd vaccine dose	n/a	n/a
No record of a previous COVID-19 vaccination [1 st dose]	Study participants will be required to have no record of a previous COVID-19 vaccination	after	[- anytime, ID]	OP	RxNorm	n/a	People with 1 st vaccine dose	n/a	n/a
At least 90days of time elapsed since the last record of a clinical diagnosis of COVID-19 or positive SARS-COV-2 test at the time of study inclusion	Study participants will be required to have no record of a clinical diagnosis of COVID-19 or positive SARS-COV-2 test within 90days before their index date	after	[-90, ID]	OP	SNOMED	n/a	All study population	n/a	n/a

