8.6 Variables

8.6.1. Exposures

Vaccination against SARS-CoV-2

COVID-19 vaccine exposure status will be defined by number of received doses, i.e. 1 dose only, completed primary vaccination course (2 doses), 3rd dose (1st booster) and 4th dose (2nd booster). For booster doses, we will distinguish between monovalent or adapted/bivalent vaccines where possible. Where such detailed information is not available in the databases, we will use the number of vaccine doses received and the vaccine brand.

Start of the respective studies will depend on when the respective vaccines became available. An overview of dates of marketing approval is provided in [Table 8.6.1.1](#) below.

Table 8.6.1.1 Marketing approval dates

Country	UK	The Netherlands	Spain
Responsible Agency	MHRA	EMA	
Comirnaty original strain (monovalent)	08/12/2020	21/12/2020 ¹⁴	
Comirnaty original strain + omicron ba1 (adapted, bivalent)	02/09/2022 ¹⁵	01/09/2022 ¹⁶	
Comirnaty original strain + omicron ba4/5 (adapted, bivalent)	09/11/2022 ¹⁷	12/09/2022 ¹⁸	
Spikevax original strain (monovalent)	31/03/2021 ¹⁹	06/01/2021 ²⁰	
Spikevax original strain + omicron ba1 (adapted, bivalent)	15/08/2022	01/09/2022	
Spikevax original strain + omicron ba4/5 (adapted, bivalent)	21/02/2023 ²¹	19/10/2022 ²²	

Table 8.6.1.1 provides an operational definition of COVID-19 exposure status.

	Phase II C3-002 – Study Protocol	
	Author(s): [name], [name], [name]	Version: v2.1
	Dissemination level: Public	

Table 8.6.1.1 Operational definition of exposure status

Exposure group name(s)	Details	Washout window	Assessment Window	Care Setting ¹	Code Type	Applied to study populations:	Incident with respect to...
Covid-19 vaccinated: 1 dose only	Exactly 1 Comirnaty/Spikevax vaccination record	Anytime in a patient's history	[-anytime, ID]	OP	RxNorm	Source population	COVID-19 vaccination
Covid-19 vaccinated: Completed primary vaccination course	Exactly 2 vaccination records, with the latest being Comirnaty/Spikevax	21 days	[-21, ID]				n/a
Covid-19 vaccinated: 3 rd dose	Exactly 3 vaccination records, with the 3 rd dose being either monovalent or any of the adapted, bivalent Comirnaty/Spikevax vaccines	90 days	[-90, ID]				n/a
Covid-19 vaccinated: 4 th dose, monovalent or adapted/bivalent	Exactly 4 vaccination records, with the latest being Comirnaty/Spikevax	90days	[-90, ID]				n/a

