8.8.3 Objectives 1-2: Vaccine effectiveness to prevent severe infection

Objectives 1 and 2 will assess the effectiveness of a 4th COVID-19 vaccine dose in people with 3 vaccine doses.

Study population

All people with a 3rd vaccine dose of Comirnaty or Spikevax will be included from the source population. Cohorts will be generated separately for Comirnaty and Spikevax, respectively.

Study inclusion: Sequential matching

Inclusion will be conducted using a sequential matching design, with similar designs being used in previous studies assessing vaccine effectiveness. Previous research showed matching to adequately reduce measured confounding in vaccine effectiveness research when including key variables such as geographic location²⁴.

Matching process using key confounders and Propensity Scores

For each calendar week starting from the day when a 4th vaccine dose (i.e. 2nd booster vaccine) became available/recommended in the respective country, people will be assigned to two cohorts: people who received a 4th vaccine dose during that week and people who did not receive a 4th dose.

Using the first day of the respective week as “preliminary” index date for non-boostered people, and the date of the 4th dose for booster-vaccinated people, the following inclusion criteria will be applied:

	Phase II C3-002 – Study Protocol	
	Author(s): [name], [name], [name]	Version: v2.1
		Dissemination level: Public

- At least 365 days of data availability in the respective database
- At least 90days of time elapsed since the previous vaccine dose (i.e. the 3rd or 4th vaccine dose)
- At least 90days of time elapsed since the last record of a clinical diagnosis of COVID-19 or positive SARS-COV-2 test.

Among those people in the cohorts who received or not received a 4th dose and met the inclusion criteria, non-boostered people will be matched 1:1 to a person receiving their 4th dose, based on key confounders and large-scale propensity scores using nearest neighbor matching, with caliper width 0.2 standard deviation. Key confounders will comprise but are not limited to:

- Age (e.g. 5-year age bands)
- Sex (exact)
- Geographic location (exact)
- Previous vaccine brands (e.g. homologous or heterologous vaccination scheme)
- Time from previous vaccination
- History of conditions for prioritization for vaccination
- immunocompromised status
- previous SARS-CoV-2 diagnosis (>90days before index date)

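### For Objectives 3-6 the operational tables leave the make of dose n-1 open in the newer-dose arm but not in its comparator, against Table 7.1, and the example brand matching does not close the gap

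*Protocol*

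**What the plan says.** Table 8.5.1 (section 8.5) defines the groups by number of records and by the make of the latest one:

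- one dose: "Exactly 1 Comirnaty/Spikevax vaccination record";
- two doses: "Exactly 2 vaccination records, with the latest being Comirnaty/Spikevax and at least 21days later than the 1st dose";
- three doses: "Exactly 3 vaccination records, with the 3 rd dose being either monovalent or any of the adapted, bivalent Comirnaty/Spikevax vaccines";
- four doses: "Exactly 4 vaccination records, with the latest being Comirnaty/Spikevax".

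The operational exposure table in section 8.6.1 (the second of two tables numbered 8.6.1.1) repeats the rule, for example "Exactly 2 vaccination records, with the latest being Comirnaty/Spikevax".

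Table 7.1 B (Objective 3) and C (Objectives 4-6) set a population condition for both arms: "a 1st-vaccine dose [2nd vaccine dose; 3rd vaccine dose] of Comirnaty or Spikevax". The exposure there is the 2nd, 3rd or 4th dose, so the condition falls on the dose before the one being studied.

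Section 8.8.3 lists, among the matching variables, "Previous vaccine brands (e.g. homologous or heterologous vaccination scheme"). Sections 8.8.4 and 8.8.5 apply the same sequential matching to Objectives 3-6.

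**The concern.** Call the newer dose n. The comparator is the (n-1)-dose group, whose latest dose is dose n-1, so the operational tables force that dose to be Comirnaty or Spikevax. In the newer-dose arm the latest dose is dose n, and nothing in those tables restricts dose n-1. The rule reads the same for every group, but it falls on a different dose in each arm of a comparison.

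A hazard ratio for one added dose should compare people whose histories are alike up to that dose. If part of the newer-dose arm received another make at dose n-1 and the paired comparators did not, the ratio also carries any difference in protection between the earlier courses. Who enters the newer-dose arm would depend on which table the programmer follows.

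**Working it through.** The protocol states no figure on this point to reproduce. The check has three steps.

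**1. Histories admitted by each rule.** Take three makes: Comirnaty, Spikevax and other. Under Table 8.5.1 alone, the newer-dose arm admits any history over doses 1 to n-1, which is 3^(n-1). The comparator admits any history whose dose n-1 is Comirnaty or Spikevax, which is 2 × 3^(n-2). The difference, 3^(n-2), is the set with another make at dose n-1 and so with no counterpart.

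| Comparison | Newer-dose arm | Comparator | No counterpart | Comparator histories with another make at any dose | Both arms with the Table 7.1 condition added |
|---|---|---|---|---|---|
| 1 vs 2 doses (n=2) | 3 | 2 | 1 | 0 of 2 | 2 and 2, identical |
| 2 vs 3 doses (n=3) | 9 | 6 | 3 | 2 of 6 | 6 and 6, identical |
| 3 vs 4 doses (n=4) | 27 | 18 | 9 | 10 of 18 | 18 and 18, identical |

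These are counts of possible histories, not of people. The fifth column shows that comparators are not free of other makes in the last two comparisons; the asymmetry sits at dose n-1 only.

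**2. Does matching on previous brands remove it?** That depends on the coding.

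- As a homologous/heterologous flag, every history without a counterpart (1 of 1, 3 of 3, 9 of 9) can be paired with a comparator of a different make. Two earlier doses of another make are homologous, and so are two of Comirnaty. A single earlier dose has no scheme at all.
- As the actual brand of each earlier dose, none of them can be paired, and those people go unmatched.

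The flag is the only form the protocol names. Sex and geographic location are marked as exact in the same list; previous brands is not.

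**3. Would anything else catch it?** The propensity score draws on co-medications and comorbidities (section 8.8.3), and vaccine make is not named. Negative control outcomes are chosen because vaccination does not cause them, so a difference in protection between earlier courses would not show there. Section 8.8.6 plans no sensitivity analyses.

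**The case against.** The strongest reply is that Table 7.1 and Table 8.5.1 can be applied together: take the Table 7.1 population first, then form dose groups. The last column above shows that the asymmetry then disappears. Section 8.8.3 follows that order for Objectives 1-2, taking people with a 3rd dose of Comirnaty or Spikevax before assigning them to arms, and Objectives 3-6 are to be derived similarly. Previous brands is itself the matching variable, the flag is only an example, and its coding could be left to the SAP.

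Much of this stands, and it makes the bias conditional. It does not settle the matter for Objectives 3-6. Section 8.5 sends the analyst to Tables 8.5.1 and 8.5.2 for operational criteria, and neither carries the condition on dose n-1. Section 8.8.4 relists the inclusion criteria without a make condition, and section 8.8.5 refers back to that list. Nor can the tables be assumed to stack: for the 2nd dose, Table 7.1 B and C ask for 90 days since the previous dose where the operational tables ask for 21. Separate analyses by brand do not close the gap either if the stratum follows the latest dose, as in the exposure table.

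A reader might infer more than the protocol supports:

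- **That comparators' earlier doses are all restricted.** This is true only for 1 vs 2 doses. Otherwise, comparators' doses before n-1 are as open as in the newer-dose arm.
- **That Objectives 1-2 are affected.** Section 8.8.3 already sets the condition for them.
- **That the comparator line in Table 7.1, "No 2 nd vaccine dose [3 rd vaccine dose; 4 th vaccine dose] of Comirnaty or Spikevax", lets in people who had dose n from another make.** The operational tables require exactly n-1 records, and section 8.5 has the counterpart one dose behind.
- **That Table 8.2.1 sizes the problem.** In SIDIAP, (6,548,545 + 3,371,395) / 5.8 million = 1.71 Comirnaty and Spikevax records per active subject. But the table does not say its feasibility counts are limited to active subjects. Turning them into a share of other makes needs an assumed mean number of doses; at 1.5 the share is 1 - 1.71/1.5 = -14%, which is impossible. An all-dose share is also not the share at dose n-1 in the newer-dose arm.

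**Conclusion.** The point holds in limited form and should be corrected. For Objectives 3-6 the protocol fixes two different rules for the make of dose n-1: Table 7.1 B and C require Comirnaty or Spikevax in both arms, while Tables 8.5.1 and 8.6.1.1 require it in the comparator only. That mismatch is in the text and needs no assumption.

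Bias in the hazard ratio needs two conditions together: the operational tables are followed without Table 7.1, and previous brands is coded as the example flag. Its direction depends on whether people primed with another make have higher or lower risk than those primed with Comirnaty or Spikevax, and the protocol does not say. No size in people or in vaccine effectiveness can be given; the 1, 3 and 9 histories without a counterpart show where the gap lies, not how often it occurs.

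**What to change.** 1. Carry the Table 7.1 condition into Tables 8.5.1 and 8.6.1.1 for both members of a pair in Objectives 3-6: dose n-1 is Comirnaty or Spikevax, as section 8.8.3 already has it for the 3rd dose in Objectives 1-2. This alone makes the admitted histories identical in the two arms.
2. In section 8.8.3, and so in 8.8.4 and 8.8.5, replace the homologous/heterologous example with exact matching on the recorded brand of each earlier dose. The first change equalises the histories admitted; this one equalises them within pairs. Brand is the right level, because section 8.2 says products (monovalent or bivalent) are not reliably recorded.

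The change is wording in two tables and one matching variable. Newer-dose people whose previous dose was another make are left out, so the results do not speak to them, and some pairs are lost to exact brand matching.

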8.6 Variables

8.6.1. Exposures

Vaccination against SARS-CoV-2

COVID-19 vaccine exposure status will be defined by number of received doses, i.e. 1 dose only, completed primary vaccination course (2 doses), 3rd dose (1st booster) and 4th dose (2nd booster). For booster doses, we will distinguish between monovalent or adapted/bivalent vaccines where possible. Where such detailed information is not available in the databases, we will use the number of vaccine doses received and the vaccine brand.

Start of the respective studies will depend on when the respective vaccines became available. An overview of dates of marketing approval is provided in [Table 8.6.1.1](#) below.

Table 8.6.1.1 Marketing approval dates

Country	UK	The Netherlands	Spain
Responsible Agency	MHRA	EMA	
Comirnaty original strain (monovalent)	08/12/2020	21/12/2020 ¹⁴	
Comirnaty original strain + omicron ba1 (adapted, bivalent)	02/09/2022 ¹⁵	01/09/2022 ¹⁶	
Comirnaty original strain + omicron ba4/5 (adapted, bivalent)	09/11/2022 ¹⁷	12/09/2022 ¹⁸	
Spikevax original strain (monovalent)	31/03/2021 ¹⁹	06/01/2021 ²⁰	
Spikevax original strain + omicron ba1 (adapted, bivalent)	15/08/2022	01/09/2022	
Spikevax original strain + omicron ba4/5 (adapted, bivalent)	21/02/2023 ²¹	19/10/2022 ²²	

Table 8.6.1.1 provides an operational definition of COVID-19 exposure status.

	Phase II C3-002 – Study Protocol	
	Author(s): [name], [name], [name]	Version: v2.1
	Dissemination level: Public	

Table 8.6.1.1 Operational definition of exposure status

Exposure group name(s)	Details	Washout window	Assessment Window	Care Setting ¹	Code Type	Applied to study populations:	Incident with respect to...
Covid-19 vaccinated: 1 dose only	Exactly 1 Comirnaty/Spikevax vaccination record	Anytime in a patient's history	[-anytime, ID]	OP	RxNorm	Source population	COVID-19 vaccination
Covid-19 vaccinated: Completed primary vaccination course	Exactly 2 vaccination records, with the latest being Comirnaty/Spikevax	21 days	[-21, ID]				n/a
Covid-19 vaccinated: 3 rd dose	Exactly 3 vaccination records, with the 3 rd dose being either monovalent or any of the adapted, bivalent Comirnaty/Spikevax vaccines	90 days	[-90, ID]				n/a
Covid-19 vaccinated: 4 th dose, monovalent or adapted/bivalent	Exactly 4 vaccination records, with the latest being Comirnaty/Spikevax	90days	[-90, ID]				n/a
Covid-19 vaccinated: 4 th dose, monovalent	Exactly 4 vaccination records, with the 4 th dose being a monovalent Comirnaty/Spikevax vaccine	90days	[-90, ID]				n/a
Covid-19 vaccinated: 4 th dose, adapted/bivalent	Exactly 4 vaccination records, with the 4 th dose being any of the adapted, bivalent Comirnaty/Spikevax vaccines	90days	[-90, ID]				n/a

	Phase II C3-002 – Study Protocol	
	Author(s): [name], [name], [name]	Version: v2.1
		Dissemination level: Public

8.6.2. Outcomes

Primary outcomes of interest:

1. COVID-19 related hospitalisation
2. COVID-19 related death
3. All-cause mortality in the 3 months after discharge from a COVID-19 hospitalisation
4. All-cause mortality in the 6 months after discharge from a COVID-19 hospitalisation
5. Incidence of new-onset type 1 Diabetes Mellitus beyond the first 30d after SARS-CoV-2 infection
6. Incidence of new-onset type 2 Diabetes Mellitus beyond the first 30d after SARS-CoV-2 infection
7. Incidence of cardiovascular events (cerebrovascular disorders, dysrhythmias, ischemic and non-ischemic heart disease, pericarditis, myocarditis, heart failure and thromboembolic disease) in the 12 months after a SARS-CoV-2 infection.

Preliminary code lists are available in the appendix of this protocol for all outcomes.

SARS-CoV-2 infection and COVID-19

Positive test result for SARS-CoV-2

RT-PCR tests have high sensitivity and specificity for SARS-CoV-2. However, as a result of changes in the availability of population wide RT-PCR and home self-reported lateral flow tests during the Omicron period, it may not be possible to exclusively use RT-PCR tests when identifying positive test results in all datasets. All positive test results for SARS-CoV-2 observable in the database will therefore be included for the primary analysis, with documentation of what type of test it was to allow sensitivity analysis restricted to RT-PCR diagnosed patients as needed.

Clinical diagnosis of COVID-19

Whilst testing for SARS-CoV-2 was commonly performed in some of the countries that will be represented in this study, clinical diagnoses of COVID-19 were also made for many individuals. Diagnostic codes compatible with COVID-19 will therefore also be identified, with the recorded date being used in the analyses.

Hospitalization with COVID-19

Patients hospitalized with COVID-19 will be identified based on having a hospitalization along with a confirmatory diagnosis or test result of COVID-19 (both as defined above) within a time window from 21 days prior to admission up to three days following their admission. This time window has been chosen in accordance with previous studies commissioned by the EMA, and aimed to include those who had the diagnosis made prior to their hospitalization and to allow for a delay in test results or diagnoses to be made or recorded, while excluding individuals with hospital-acquired COVID-19.

COVID-19 related death

COVID-19 related death will be defined as death within 28 days from the date of COVID-19 clinical diagnosis or positive SARS-CoV-2 test.

	Phase II C3-002 – Study Protocol	
	Author(s): [name], [name], [name]	Version: v2.1
	Dissemination level: Public	

All-cause mortality

[figure not shown]
Death from any cause will be assessed from the date of death recorded in primary care records or from linked mortality information.

Post-acute COVID-19 complications

New-onset type 1 Diabetes Mellitus following SARS-COV-2 infection

New onset type 1 diabetes following SARS-COV-2 infection will be defined e.g. as a new diagnosis of Type 1 diabetes or prescription of insulin without concomitant use of other antidiabetic drugs within 30days-365days following SARS-CoV-2 positive test or clinical COVID-19 diagnosis. People with a previous recording of diabetes of any type, including HbA1c >6.5%, will not be included for objectives 4 and 5.

Figure 8.6.2.1 Illustrates the algorithm for the outcome definition of New-onset type 1 Diabetes Mellitus following SARS-COV-2 infection

	Phase II C3-002 – Study Protocol	
	Author(s): [name], [name], [name]	Version: v2.1
		Dissemination level: Public

New-onset type 2 Diabetes Mellitus following SARS-COV-2 infection

New onset type 2 diabetes following SARS-COV-2 infection will be defined as e.g. a new diagnosis of Type 2 diabetes or initiation of an oral antidiabetic medicine (e.g. metformin) within 30days-365days following SARS-CoV-2 positive test or clinical COVID-19 diagnosis. People with a previous recording of diabetes of any type, including HbA1c >6.5%, will not be included for objectives 4 and 5.

Phenotypes for Type 1 and Type 2 Diabetes Mellitus will be developed and tested across all databases before using the definition in this study. Plausibility test will be conducted using CohortDiagnostics, including the review of patient characteristics (e.g. demographics, comorbidities and previous comedication) for people identified with new onset diabetes.

Cardiovascular events

Cardiovascular events will be evaluated as a composite outcome and stratified for relevant subgroups:

Major cardiovascular events (MACE): will be identified by diagnostic codes for heart failure, acute myocardial infarction, stroke, or the occurrence of sudden cardiac death.

Venous thromboembolic events: will be identified by diagnostic codes for pulmonary embolism or deep vein thrombosis.

Arterial thromboembolic events: will be identified by an acute myocardial infarction or acute ischemic stroke.

Cerebrovascular disorders will be identified by acute ischemic stroke, haemorrhagic stroke or transient ischemic attack.

Heart failure, cardiac arrhythmia, angina pectoris, pericarditis and myocarditis will be measured as outcomes.

Phenotypes for these outcomes have been developed and used in previous vaccine safety studies^{13,13}. Code lists are available in the appendix of this protocol.

	Phase II C3-002 – Study Protocol	
	Author(s): [name], [name], [name]	Version: v2
	Dissemination level: Public	

Table 8.6.2.1 Operational Definitions of Outcome

Outcome name	Details	Primary outcome ?	Type of outcome	Washout window	Care Settings ¹	Code Type	Diagnosis Position ²	Applied to study:	Measurement characteristics/ validation	Source of algorithm
Hospitalization with COVID-19	COVID-19 clinical diagnosis or SARS-CoV-2 positive test within a time window from 21 days prior to admission to 3 days after hospital admission	Yes	Binary, time-to-event	n/a	IP, OP	SNOMED	any	Cohort 1-4	n/a	n/a
COVID-19 related death	COVID-19 clinical diagnosis or SARS-CoV-2 positive test up to 28days prior to date of death	Yes	Binary, time-to-event	n/a	OP		n/a	Cohort 1-4	n/a	n/a
All-cause mortality	date of death	Yes	Binary, time-to-event	n/a	OP		n/a	Cohort 5-8	n/a	n/a
New-onset type 1 Diabetes Mellitus	New onset Type 1 Diabetes Mellitus within 30-365days following SARS-CoV-2 positive test or COVID-19 diagnosis	Yes	Binary, time-to-event	Anytime prior ID	OP		n/a	Cohort 5-8	n/a	n/a
New-onset type 2 Diabetes Mellitus	New onset Type 2 Diabetes Mellitus within 30-365days following SARS-CoV-2 positive test or COVID-19 diagnosis	Yes	Binary, time-to-event	Anytime prior ID	OP		n/a	Cohort 5-8	n/a	n/a
Cardiovascular events	New Cardiovascular event/complication recorded within 30-365days following SARS-CoV-2 positive test or COVID-19 diagnosis	Yes	Binary, time-to-event	365days prior to index date	OP		n/a	Cohort 5-8	n/a	¹³

OP = outpatient, n/a = not applicable

This document represents the views of the DARWIN EU® Coordination Centre only and cannot be interpreted as reflecting those of the European Medicines Agency or the European Medicines Regulatory Network.

	Phase II C3-002 – Study Protocol	
	Author(s): [name], [name], [name]	Version: v2
		Dissemination level: Public

8.6.3. Other covariates, including confounders, effect modifiers and other variables (where relevant)

Demographics

Patients' age at index date and sex will be identified.

Geographic location

We will use geographic location, e.g. GP surgery or healthcare regions to account for local vaccination, infection and testing rates.

Predominant SARS-CoV-2 variant

Calendar time will be used as a proxy to define exposure to the predominant variant, including "Alpha and earlier variants", "Delta", "Omicron" and "XBB variant or later dominant" for databases with sufficient recent data. Time periods are specified in section 8.3 Study Period.

Health conditions pre-index date

Individuals' history of the comorbidities will be identified over three time periods prior to the index date, and will be used for summary characterisation and calculation of large-scale propensity scores:

- 1) 30 days prior to one day prior index date,
- 2) 365 days prior to one day prior index date,
- 3) all available days observed up to one day prior to index date.

A range of health conditions will be assessed using the time windows above. Among these, the following conditions will be identified for summary characterisation: anxiety, asthma, chronic obstructive pulmonary disease, chronic kidney disease, chronic liver disease, COVID-19, atrial fibrillation, cancer (excluding non-melanoma skin cancers), dementia, depressive disorder, diabetes, GERD, heart failure, hypertension, hypothyroidism, inflammatory bowel disease (crohn's disease or ulcerative colitis), myocardial infarction, venous thromboembolism, stroke, transient ischaemic attack (TIA), rheumatoid arthritis, osteoporosis, alcohol or drug substance misuse and obesity.

Medications pre-index date

Pre-existing medication use will be identified using 2 time windows, defined as 365 days to one day prior to index date, and 30 days to 1 day prior to index date, and will be used to provide summary characterisation for patients and calculation of large-scale propensity scores.

Immunocompromised status at the index date

People who are immunocompromised at the index data will be defined by the recording of certain conditions or certain conditions plus treatments prior to index date. People will be considered immunocompromised if they have *one or more* of the following conditions recorded within 365 days prior to index date:

	Phase II C3-002 – Study Protocol	
	Author(s): [name], [name], [name]	Version: v2.1
		Dissemination level: Public

- HIV/AIDS,
- Hematological malignancies
- Solid malignancies
- Other intrinsic immune conditions

People will be defined as being immunocompromised if they are treated with antineoplastic and immunomodulating agents between 183 days to one day prior to index date. People will also be defined as being immunocompromised if they are treated with systemic corticosteroids between 183 days to one day prior to index date and have a recording of the following within 365 days prior to index date:

- Organ transplantations
- Rheumatologic/inflammatory conditions (rheumatoid arthritis, inflammatory bowel disease, and systemic lupus erythematosus)

The same algorithm/phenotype has been used in DARWIN EU Study P2-C3-001.

History of conditions for prioritization for vaccination

Additional conditions used for the identification of priority groups for vaccination not mentioned in any of the lists above (e.g. pregnancy) will be included.

	Phase II C3-002 – Study Protocol	
	Author(s): [name], [name], [name]	Version: v2
	Dissemination level: Public	

Table 7. Operational Definitions of Covariates

Characteristic	Details	Type of variable	Assessment window	Care Settings ¹	Code Type	Diagnosis Position ²	Applied to study populations:	Measurement characteristics/validation	Source for algorithm
Demographics	Age and sex at index date	Numeric, binary	All history	OP		N/A	All cohort	n/a	n/a
Geographic location	Location identifier of GP surgery, healthcare regions	Categorical	All history	OP		N/A	All cohort	n/a	n/a
Predominant SARS-CoV-2 variant	Calendar time as proxy for predominant variant, including “Alpha and earlier variants”, “Delta”, “Omicron” and “XBB variant or later dominant”	Categorical	All history	OP		N/A	All cohort	n/a	n/a
Co-morbidity	Conditions of interest prior to index date	Binary	All history	OP	SNOMED	N/A	All cohort	n/a	n/a
Co-medication	Drug prescriptions prior to index date	Binary	[-183,-1] [-31 -1]	OP	RxNorm	N/A	All cohort	n/a	n/a
Immuno-compromised status	1.) Recording of Conditions: HIV/AIDS, Hematological malignancies, Solid malignancies, Other intrinsic immune conditions 2.) Treatment with antineoplastic and immunomodulating agents 3.) Systemic corticosteroids between 183 days to one day prior to index date + recording of organ transplantations, rheumatologic/inflammatory conditions within 365 days prior to index date	binary	[-365, -1] for condition, [-183,-1] for treatment	OP	SNOMED, RxNorm	N/A	All cohort	n/a	n/a

¹ IP = inpatient, OP = outpatient, ED = emergency department, OT = other, n/a = not applicable

	Phase II C3-002 – Study Protocol	
	Author(s): [name], [name], [name]	Version: v2
		Dissemination level: Public

